6.1.2 Per-protocol set

Per-protocol set (PPS): The set that conforms to inclusion criteria, does not conform to exclusion criteria and completes therapeutic schedule. Do analysis (PP analysis) to cases that are fit to experiment program, with good compliance, not taking any prohibited drug and complete required contents of CRF.

PP population is the secondary population for curative evaluation in this study.

6.1.3 Safety set (SS)

Safety set (SS): The actual data that patients accept at least one time treatment with safety indexes recording. Do not do data-carry-forward if safety is missing; the incidence of adverse events takes the number of safety set as denominator.

SS population is the main population for safety evaluation in this study.

6.2 Statistical method

6.2.1 General principle

SAS9.4 software is adopted for statistical analysis. All data are performed with two-sided test, and P value less than or equal to 0.05 (two-sided test) is considered with statistical difference. (Unless the special instruction)

Quantitative indexes are described with case number, mean, standard deviation, median, P25 (Q1), P75(Q3), minimum value (Min) and maximum value (Max).

Classification indexes are described with case number and percentage.

Comparison of general situation should be analyzed with appropriate method based on the type of indexes. Quantitative data should be analyzed with paired t test or Wilcoxon rank sum test; classification data with chi-square test or precise probability method, and ranked data with Wilcoxon rank-sum test or CMH test.

6.2.2 Completion of study

Summarize the number of enrollment and completion of each center, completion of enrollment in treatment group and control group, and size of different data sets; make a list of drop-out case and distribution of cases in each center.

6.2.3 Demographic description and baseline description

Describe the demographic characteristics of subjects (e.g. age, sex, marital status, body height, body weight, nationality, job category), medical history, past history, imaging examination, therapeutic condition, drug combination, and so on, according to general principles, and evaluate the comparability between the two groups with inter-group comparison.

Analysis on drug compliance: Observe the detailed record of drug distribution and recovery to determine the compliance of subjects; if the actual dosage is within 80-120% of predicted dosage, the drug compliance conforms to the requirement of programme. Compare whether the patients of the two groups take investigational medicine on time and don't taking prohibited medicine and food of the scheme.

Study No.: Document No.:

6.2.4 Efficiency evaluation

Baseline efficiency: Describe the baseline of each curative index, and comparison between groups should be made in accordance with general condition. Modified Rankin (mRS) score is regarded as ranked data, and should be compared with Wilcoxon rank sum test. NIHSS score should be regarded as quantitative data and ranked data (4-7 points, 8-14 points and 15-22 points) for description and comparison; BI score as quantitative data and enumeration data (<85 points, ≥85 points) for description and comparison.

Primary efficiency indexes:

PP analysis and FAS analysis should be performed at the same time; evaluation on patients with modified Rankin (mRS) score≤1 should be mainly conducted ontaken at day 90 day (PP set) and the time for suspending and drop-out (FAS set). Primary indexes should be compared between the two groups with CMH-γ2 method for controlling central effect.

Superiority test is adopted for primary indexes, and the hypotheses under test are as follows:

$$H_0$$
: $\pi_{\text{treatment group}} - \pi_{\text{control group}} \le 0$

$$H_1: \pi_{\text{treatment group}} - \pi_{\text{control group}} > 0$$

$$\alpha = 0.025_{\text{(one-sided)}}$$

The treatment group is superior to control group, if H0 is rejected under α level, or lower limit of 95% Cl for difference of retention rate between the two groups is higher than 0. Take sensitivity analysis on primary efficiency indexes with modified Rankin (mRS) score≤2 points as the limit.

Other secondary indexes can be statistically analyzed in accordance with methods for primary indexes.

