4.2. Number of cases, grouping and study centers

According to the China National Stroke Registry (CNSR), 39.59% of patients with NIHSS Page 7 of 76

score of 4–22 at admission had mRS \leq 1 at 3 months. Assuming a 40% proportion of patients with mRS \leq 1 at 90 days in the control group and a 47% proportion in the treatment group, with an equal ratio design, and utilizing PASS 2008 to calculate the required sample size, with α = 0.05 (two-sided test) and β = 0.2 (test power 80%), the calculated sample size for both the treatment and control groups is 787 cases. To account for potential dropouts in clinical studies, an additional 20% of the sample size is added. Therefore, a total of 1,968 patients are planned to be included in this study.

Patients will be allocated in a 1:1 ratio to the treatment group and the control group, and the study is planned to be conducted at 50 centers nationwide.

5. Study Population

Patients entering the study must meet all the inclusion criteria listed below and must not meet any of the exclusion criteria. In addition to the criteria listed below, any medical conditions or use of prohibited medications during the standard treatment that are considered contraindications will also be grounds for excluding patients from the study.

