6.1.1 Full analysis set (FAS)

Full analysis set (FAS) or modified intention-to-treat (ITT): Set of all the patients who underwent randomization, given any treatment, and underwent any posttreatment assessment. When main indexes of curative effect are missing, the set should be supplemented with last observation carried forward (LOCF) on the basis of intention to treat (ITT). Comparability analysis and the missing value of secondary effect indexes don't need data-carry-forward. Take analysis on actual data in FAS.

FAS population is the main population for curative evaluation in this study.

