7.3 Efficiency evaluation

7.3.1 Baseline effect indexes

Table 7.3.1.1 Baseline mRS score

		FAS	FAS		PPS	
		Treatment		Treatment	Control	
Item	Index	group	Control group	group	group	
Baseline NIHSS score	N(Missing)					
	Mean(SD)					
	Median					
	Q1,Q3					
	Min, Max					
	Statistics					
	P value					

Table 7.3.1.2 Baseline NIHSS score – as quantitative data

		FAS	PPS		
		Treatment		Treatment	
Item	Index	group	Control group	group	Control group
Baseline NIHSS score	N(Missing)				_
	Mean(SD)				

Study No.: Document No.:

			FAS		PPS	
		Treatment		Treatment		
Item	Index	group	Control group	group	Control group	
	Median				_	
	Q1,Q3					
	Min, Max					
	Statistics					
	P value					

Table 7.3.1.3 Baseline NIHSS score – as ranked data

		FAS		PPS	
		Treatment		Treatment	
Item	Index	group	Control group	group	Control group
Baseline NIHSS score	4-7 points n (%)				
	8-14 points n (%)				
	15-22 points n (%)				
	N (Missing)				
	Statistics				
	P value				

Table 7.3.1.4 Baseline BI score – as quantitative data

		FAS		PPS	_
		Treatment		Treatment	
Item	Index	group	Control group	group	Control group
	N(Missing)				_
Baseline BI score	Mean(SD)				
	Median				
	Q1,Q3				
	Min, Max				
	Statistics				
	P value				

Table 7.3.1.5 Baseline BI score – as enumeration data

		FAS		PPS	
		Treatment		Treatment	
Item	Index	group	Control group	group	Control group
Baseline BI score	<85 points n(%)				
	≥85 points n(%)				
	N (Missing)				
	Statistics				
	P value				
	P value				

7.3.2 Primary effect index - Improvement of daily life ability at 90 days after treatment Table 7.3.2.1 Improvement of daily life ability at 90 days after treatment

		FAS		PPS	
		Treatment		Treatment	_
Item	Index	group	Control group	group	Control group
	≤1 point n(%)				
mRS score at 90 days after	>1 point n(%)				
treatment					
	N (Missing)				
	Statistics				
	P value				
	Rate difference				
	95%CI				

Note: 1. Take CMH- χ^2 test to control central effect

2. Statistical description of baseline mRS score see Table 7.3.1.1

Table 7.3.2.2 Improvement of daily life ability at 90 days after treatment – take mRS=2 as limit

		FAS		PPS	
		Treatment		Treatment	_
Item	Index	group	Control group	group	Control group
	≤2 point n(%)				
mRS score at 90 days after	>2 point n(%)				
treatment					
	N (Missing)				
	Statistics				
	P value				
	95%CI				

Note: 1. Take CMH- χ^2 test to control central effect

2. Statistical description of baseline mRS score see Table 7.3.1.1

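### The only labelled sensitivity analysis of the primary moves the cut-off to mRS ≤2; no FAS analysis at mRS ≤1 varies the LOCF assumption

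*Combined protocol and SAP*

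**What the plan says.** The primary endpoint is the proportion with mRS ≤1 at 90 days. SAP 6.1.1 makes the FAS the main efficacy population and, where the primary outcome is missing, says "the set should be supplemented with last observation carried forward (LOCF"). Protocol 12.1 also names LOCF. SAP 6.2.4 evaluates the FAS at the time of discontinuation or dropout, and the per-protocol set (PPS) at Day 90.

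SAP 6.2.4 then gives the one analysis labelled as a sensitivity analysis: "Take sensitivity analysis on primary efficiency indexes with modified Rankin (mRS", with a score of 2 or below as the limit. Its shell, Table 7.3.2.2 ("take mRS=2 as limit"), has FAS and PPS columns. Sections 6 and 7 of the SAP contain no observed-case, missing-as-failure, multiple-imputation, worst-case or tipping-point analysis of mRS ≤1 in the FAS.

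SAP 6.1.1 analyses secondary endpoints on actual data, without carry-forward. One of them is the disability rate, mRS ≥3 at 90 days (SAP 5.2), the exact complement of mRS ≤2.

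On dropout, protocol 4.2 says: "To account for potential dropouts in clinical studies, an additional 20% of the sample size is added".

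**The concern.** A sensitivity analysis should hold the question fixed and vary an assumption on which the answer rests. Moving the cut-off changes the question and leaves the missing-data assumption alone. A patient carried forward at mRS 0 or 1 is a success at both cut-offs, so the mRS ≤2 analysis cannot expose an error in that score.

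The assumption is a substantial one here. The last scheduled mRS before Day 90 is at discharge, or on Day 21 if the stay is longer. Under the visit schedule a carried-forward score is therefore at least about 90 − 21 = 69 days early, in a condition where function changes over those weeks. The listed reasons for dropout (protocol 5.3) include adverse events, lack of efficacy and endovascular therapy, which may be related to outcome. The mRS in Appendix 2 stops at level 5 and the plan does not say how a death is scored. If a death were treated as missing, an early score of 0 or 1 would be carried forward as a success.

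At stake is a report that calls the primary result supported by sensitivity analysis when its dependence on LOCF was never examined.

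**Working it through.** **Inputs (protocol 4.2).** "Assuming a 40% proportion of patients with mRS" ≤1 in the control group and "a 47% proportion in the treatment group"; "with α = 0.05 (two-sided test) and β = 0.2 (test power 80"%); "the calculated sample size for both the treatment and control groups is 787 cases"; 1,968 patients in total, 1:1.

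**The plan's own figures.** With pooled variance, no continuity correction and mean rate 0.435:

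n = [1.96·√(2·0.435·0.565) + 0.8416·√(0.40·0.60 + 0.47·0.53)]² / 0.07² = 786.2, so 787 per arm.

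787 / (1 − 0.20) = 983.75, so 984 per arm and 1,968 in total. Both figures reproduce. The 20% is thus a share of enrolled patients, 984 − 787 = 197 per arm.

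**Check 1: how much scoring error removes significance.** Suppose the LOCF-completed FAS shows 47% v 40% with 984 per arm, ignoring centre.

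- SE = √[(0.47·0.53 + 0.40·0.60) / 984] = 0.0223
- Smallest significant difference = 1.96 × 0.0223 = 4.37 points
- Slack = 7.00 − 4.37 = 2.63 points

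If a fraction m of each arm is imputed, and success among them is overstated by b more points in treated than in control patients, the difference is inflated by m·b. Significance is lost when b exceeds 2.63 / m:

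| Missing Day-90 mRS (assumed) | b at which significance is lost |
|---|---|
| 20% | 13 points |
| 10% | 26 points |
| 5% | 53 points |

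**Check 2: false-positive rate with no drug effect.** Take 40% in both arms. SE₀ = √(2·0.40·0.60 / 984) = 0.0221, and the one-sided error is 1 − Φ(1.96 − m·b/SE₀). With b = 10 points (an assumption):

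| Missing | Shift m·b | Shift / SE₀ | One-sided error |
|---|---|---|---|
| 20% | 2.0 points | 0.906 | 0.146 |
| 10% | 1.0 point | 0.453 | 0.066 |
| 5% | 0.5 point | 0.226 | 0.041 |

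At 20% missing, b = 5 gives 0.066 and b = 15 gives 0.274.

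**Check 3: what a tipping-point table would show.** Let patients with a Day-90 score respond at 47% v 40% and missing controls at 40%, with equal missingness by arm and a pooled two-proportion test on 984 per arm. Significance is lost once missing treated patients respond at about 33% or lower (20% missing), 29% (15% missing) or 20% (10% missing). At 5% missing there is no such rate. Only more extreme scenarios remove significance there: the worst-case bound is +1.7 points, p = 0.45. With 20% missing, counting every missing patient as a failure gives 5.6 points, p = 0.009.

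**The case against.** The strongest reply is that the plan does hold other evidence. The PPS analyses mRS ≤1 at Day 90 in patients who completed treatment. The mRS ≥3 secondary uses observed FAS data, so setting it against the FAS column of Table 7.3.2.2 would contrast LOCF with observed cases. A reader might otherwise infer that nothing in the plan bears on missing data; that is too strong. Neither analysis does the job, however. The PPS also removes patients for eligibility, compliance, prohibited drugs and incomplete CRFs, so a difference from the FAS has several possible causes. The mRS ≥3 contrast is at another cut-off, covers only the observed-case assumption, and is never planned as a comparison. It also requires that the FAS column of Table 7.3.2.2 uses LOCF, which is a reasonable inference but not stated, and cannot apply to the PPS column.

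A second reply concerns quantity. A reader might infer that up to 20% of Day-90 scores will be missing and 197 per arm imputed. The documents do not say so. The 20% is a planning allowance, not a ceiling. A dropout is anyone who does not complete the procedures (protocol 5.3). Patients who stop the drug should still complete the 3-month follow-up (protocol 6.1.6.3). The SAP's FAS also leaves out patients with no post-treatment assessment. This stands, and it is why the results are shown over a range of missing rates.

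Third, the trial is double-blind and one LOCF rule serves both arms, so a large difference in scoring error between arms is not to be presumed. That also stands: b is an assumption throughout.

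**Conclusion.** The gap is real: no planned FAS analysis at mRS ≤1 varies the LOCF assumption, and the analysis carrying the sensitivity label cannot test it. Its importance depends on a missing rate that the documents do not forecast. At 20% missing, a relative overstatement of about 13 points turns a 47% v 40% result non-significant, and 10 points under the null raises the one-sided error to about 15%. At 5% missing the figures are about 53 points and 4%, a minor matter. These results assume equal missingness by arm, the design rates, 984 per arm and no centre effect.

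A reader might go further and infer that the whole treatment effect could come from how dropouts are scored. The numbers do not support that: even at 20% missing, removing all 7 points needs a differential of 7 / 0.20 = 35 points, and 13 points only crosses the significance line. Nor do the documents show that LOCF would favour the drug. The finding is that the plan would not reveal it either way. It should be corrected because the remedy is cheap.

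**What to change.** Stop calling the mRS ≤2 analysis a sensitivity analysis. Keep it as supplementary, note that it repeats the mRS ≥3 secondary contrast, and state which missing-data rule each of the two uses.

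Before the first unblinding, specify for mRS ≤1 at Day 90 in the FAS at least one analysis that varies the missing-data assumption. Known deaths should be counted as failures and not imputed. Preferred are:

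- multiple imputation by arm, using baseline NIHSS, thrombolysis, and Day-7 and discharge mRS;
- a tipping-point table over assumed success rates among missing patients in each arm, with missing-as-failure as one entry, reporting where the conclusion changes.

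One of these would close the gap; together they show both a plausible estimate and its breaking point. All the inputs are already collected. The cost is SAP wording and some extra programming, and the result may look less robust than under LOCF alone.

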6.2.5 Safety analysis

Adverse events are described with case number, times and incidence of various adverse events, and $\chi 2$ test or Fisher's exact test is adopted for comparing the incidence between the two groups. At the same time, make a detailed list to describe the specific manifestation and extent of all adverse events and serious adverse events and their relation with drugs.

Statistically describe the vital signs at baseline and 90 days after treatment according to general principles, and make comparison between former and later times and inter-group comparison.

Make description of number of normal cases before treatment, number abnormal cases after treatment and their ratios in two groups, respectively, and $\chi 2$ test or Fisher's exact test is adopted for comparing the ratio between the two groups.

Make description of number of normal cases before treatment, number abnormal cases after treatment and their ratios in two groups, respectively, and $\chi 2$ test or Fisher's exact test is adopted for comparing the ratio between the two groups. Crosstab is adopted to describe the change of laboratory indexes before and after treatment for determining the clinical significance of these indexes.

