The primary indicator will be assessed using a superiority test, testing the following hypothesis:

$$H_0: \pi_{Test\ group} - \pi_{Control\ group} \le 0$$

$$H_1: \pi_{Test\ group} - \pi_{Control\ group} > 0$$

$$\alpha = 0.025 (One - sided)$$

If the H_0 is rejected at the significance α level, or if the lower limit of the 95% CI for the difference in retention rates between the two groups is greater than 0, it can be considered that the treatment group is superior to the control group.

Other secondary indicators will be compared using the same statistical method as the primary indicator.

12.2.4. Safety evaluation:

Describe the number and proportion of subjects with normal values before treatment and abnormal values after treatment for both the treatment group and the control group separately. Describe adverse events using the number of cases, the number of subjects, and the incidence rate. Conduct inter-group significance tests will be conducted on the incidence rate. Additionally, provide a detailed description of the specific manifestations, severity, and the relationship with the drug for all adverse events observed in each group. Provide a cross-tabular description of the changes in laboratory indicators before and after the treatment. Compare vital sign indicators before and after the treatment.

13 Data Management

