7.4 Safety evaluation

7.4.1 Adverse event

Table 7.4.1.1 Inter-group comparison of incidence of adverse events

	Treatment group		Contro	ol group			
	Case	Case		Case	Case		
Item	times	number	Percentage	times	number	Percentage	P value
Adverse events							
Adverse events related to study drugs							
Serious adverse events							
Adverse events causing drop-out							
Severe adverse events							
Severe adverse events related to study							
drugs							

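### Adverse-event and laboratory/ECG shift tables compare the arms by P value alone; a rate difference with 95% CI should be added, because non-significance does not show what excess harm is excluded

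*Combined protocol and SAP*

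**What the plan says.** Safety against placebo is among the secondary objectives in both documents (Protocol 2, SAP 3). SAP 6.2.5 sets out the analysis:

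- **Adverse events.** "Adverse events are described with case number, times and incidence of various adverse events", and for the comparison a chi-square test or "Fisher's exact test is adopted for comparing the incidence between the two groups".
- **Normal-to-abnormal shifts.** Counts and proportions per arm, then a chi-square test or "Fisher's exact test is adopted for comparing the ratio between the two groups".
- **Other output.** A listing of all AEs and SAEs (manifestation, extent, relation to drug) and before/after crosstabs of laboratory results.

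The only rule for reading these P values is the general one in SAP 6.2.1: "P value less than or equal to 0.05 (two-sided test) is considered with statistical difference". Protocol 12.2.4 is in the same vein: "Conduct inter-group significance tests will be conducted on the incidence rate".

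The shells follow the text. "Table 7.4.1.1 Inter-group comparison of incidence of adverse events" has case times, case numbers and percentages per arm, and one P value. Its rows are all aggregates: any AE, drug-related, serious, leading to drop-out, severe, and severe drug-related. Tables 7.4.3.1 to 7.4.3.7 have case number, percentage and P value. By contrast, the primary efficacy shell (SAP Table 7.3.2.1) has a row for "Rate difference" and one for its 95% CI. The closing sentence of SAP 6.2.4 extends the primary method to the secondary efficacy indexes. Safety indexes are listed separately, in SAP 5.3, and are not covered.

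**The concern.** A safety objective asks how much excess harm the data leave open. A P value does not answer that; an interval for the difference does. The trial was sized for 40% vs 47% on mRS 0 to 1, and no safety power or precision is stated. For an uncommon harm, P above 0.05 is therefore a likely result even when the drug truly doubles the rate. If the report gives only counts, percentages and P, a reader has nothing pre-specified to guard against taking non-significance as comparable safety.

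**Working it through.** **1. The plan's own figure.** Inputs (Protocol 4.2, SAP 4.4): 40% vs 47%, two-sided alpha 0.05, power 80%, 1:1 allocation, 20% dropout.

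n = [1.96·√(2·0.435·0.565) + 0.8416·√(0.40·0.60 + 0.47·0.53)]² / 0.07² = (1.3741 + 0.5886)² / 0.0049 ≈ 786.2, so 787 per arm. Then 787/0.8 = 983.75, so 984 per arm and 1,968 in total. The stated sample size reproduces and is not in dispute.

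**2. Chance of missing a true doubling.** Assumptions: 984 per arm in the Safety Set, and control rates from 0.5% to 3%, since the documents give none. Method: enumerate both binomial distributions and sum the probability that the test gives P ≤ 0.05 (uncorrected pooled chi-square, or Fisher). One minus that sum is the chance of a miss.

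| Control vs treatment | Missed, chi-square | Missed, Fisher |
|---|---|---|
| 0.5% vs 1% | 76% | 83% |
| 1% vs 2% | 54% | 62% |
| 1.5% vs 3% | 37% | 44% |
| 2% vs 4% | 25% | 30% |
| 3% vs 6% | 10% | 12% |

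Hand check at 1% vs 2% by the normal approximation:

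- Null standard error: √(2·0.015·0.985/984) = 0.00548.
- Alternative standard error: √((0.0099 + 0.0196)/984) = 0.005475.
- z = (0.01 − 1.96·0.00548)/0.005475 = −0.135, so power is about 0.446. Exact enumeration gives 0.455.

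By the same approximation, power passes 50% at a control rate of about 1.2% and 80% at about 2.3%.

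**3. What an interval would add.** Take 20/984 on treatment vs 10/984 on control, as an illustration rather than a forecast.

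- Difference = 10/984 = 1.02 percentage points.
- Pooled rate = 30/1968 = 0.01524; z = 0.010163/√(0.01524·0.98476·2/984) = 1.84; chi-square P = 0.066, Fisher P = 0.096.
- Wilson limits: 1.32% to 3.12% (treatment) and 0.55% to 1.86% (control).
- Newcombe lower limit: 1.02 − √((2.03 − 1.32)² + (1.86 − 1.02)²) ≈ −0.09 points.
- Newcombe upper limit: 1.02 + √((3.12 − 2.03)² + (1.02 − 0.55)²) ≈ +2.20 points.

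Under the 0.05 rule this is not a statistical difference, yet an excess of up to about 2.2 points is not excluded (score 95% CI for the risk ratio: 0.96 to 4.18).

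**4. What an interval would not add.** It leaves power unchanged. The formula in step 1 gives about 2,319 per arm for 80% power at 1% vs 2%, and 4,673 at 0.5% vs 1%.

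**The case against.** Several objections have weight.

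- **No rule equates non-significance with safety.** A reader might infer that the sponsor will report no difference whenever P exceeds 0.05. The documents do not say so. The 0.05 rule is a general convention, and Protocol 10.3 (five-level causality), the listings and the crosstabs also inform a safety judgment. This stands. What remains is that none of these quantifies the between-arm excess.
- **Low power is confined to uncommon harms.** A reader might infer that a doubling would usually be missed for AEs, SAEs and laboratory findings in general. The calculation does not support that: more misses than hits occur only at control rates up to about 1.2%, and from 5% to 10% a doubling is detected about 99% of the time. Nothing suggests that the aggregate rows sit near 1%. The documents' background figures are 10% to 15% stroke mortality (Protocol 3) and 8.5% to 30% hemorrhagic transformation, with symptomatic cases at 1.5% to 5% (Appendix 7). These are general stroke figures that the exclusions may lower, but only the low end of the symptomatic range enters the weak region.
- **787 per arm is a poor denominator.** Using it would worsen the figures, for example to 62% missed at 1% vs 2%. But patients who drop out after dosing and a safety assessment stay in the Safety Set, so 984 is the better approximation.
- **Aggregate rows cannot bound a specific event.** Intervals on Table 7.4.1.1 alone would say nothing about one uncommon term. This stands, and the change below extends to individual terms.
- **Readers can compute the interval themselves.** They can, from the counts. That does not pre-specify what the trial will estimate or cite.
- **Intervals exist elsewhere in the safety section.** The vital-sign change table (7.4.2.1) has a 95% CI row, without saying whether it is within or between arms. It does not reach AEs or shifts.

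**Conclusion.** The point holds as a reporting gap in the safety analysis. For AEs, SAEs and laboratory/ECG shifts, the only planned between-arm statistic is a chi-square or Fisher P value, with no rate difference or interval, although the SAP uses both for its primary endpoint. The gap matters most for harms with control rates of roughly 2% or less, where a true doubling is missed in 25% (2% vs 4%) to 76% (0.5% vs 1%) of trials by chi-square. At 3% or more a doubling is adequately detected. These figures rest on assumed control rates and about 984 per arm in the Safety Set. The low power comes from the trial's size, not from the choice of test. The primary result is unaffected; what changes is how far the trial can speak to its own safety objective.

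**What to change.** In SAP 6.2.5 and the matching shells:

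- Add the rate difference (treatment minus control) with a two-sided 95% CI, naming the method (for example Newcombe), to every row of Table 7.4.1.1 and to the shift rows of Tables 7.4.3.1 to 7.4.3.7.
- Do the same for each individual adverse-event term whose incidence is compared under 6.2.5. Include hemorrhagic events, which Protocol 10.4.2 requires to be reported as AE/SAE.
- Keep the P values, labelled descriptive.
- State that P above 0.05 is not evidence of comparable safety, and that safety statements will cite the interval.

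The cost is SAP wording and extra table columns, with no new data, patients or procedures. The downsides are many intervals unadjusted for multiplicity, and a safety statement that looks less favourable for rare events because the upper limit is visible. No acceptable excess is set here; that is a clinical judgment.
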